#### 4.1. Protocol Deviations

- Protocol deviations will be tracked by the study team throughout the conduct of the study in accordance with the Protocol Deviation Management Plan (PDMP).
- Data will be reviewed prior to Source Data Lock (SDL) to ensure all important deviations and deviations which lead to exclusion from the Per Protocol analysis population are agreed prior to unblinding. Important deviations will be categorised in the SDTM data set. Deviations leading to exclusion from the Per Protocol population will be categorised in the ADaM data set.
- Important protocol deviations (including deviations related to study inclusion/exclusion criteria, conduct of the trial, patient management or patient assessment) will be summarised and listed.
- A separate summary and listing of all inclusion/exclusion criteria deviations will also be provided. This summary will be based on data as recorded on the inclusion/exclusion page of the eCRF.
- Important protocol deviations which result in exclusion from the Per Protocol population will be summarised and listed (see [Appendix 1](#): Protocol Deviation Management and Definitions for Per Protocol Population).

## 5. CONSIDERATIONS FOR DATA ANALYSES AND DATA HANDLING CONVENTIONS

### 5.1. Study Treatment & Sub-group Display Descriptors

Treatment Group Descriptions			
RandAll NG		Data Displays for Reporting	
Code	Description	Description	Order 
A	Mepolizumab 300mg SC	Mepolizumab 300mg SC	2
P	Placebo	Placebo	1

#### NOTES:

1. Order represents treatments being presented in Tables, Figures and Listings (TFLs), as appropriate.

### 5.2. Baseline Definitions

- Baseline will be defined for all subjects in the ITT population.
- For the BFI item 3 which is collected daily from the screening visit (Visit 1) the mean of the 7 daily assessments of BFI item 3 up to but not including the date of first dose of study treatment will be used as the baseline assessment.
- For blood eosinophils, baseline will be defined as the latest central laboratory result prior to the first dose of study treatment. Investigators were permitted to use local laboratory results to meet inclusion criteria, however local laboratory results will not be used in the derivation of the baseline blood eosinophil value.
- For all other endpoints the baseline values for each assessment will be the latest available assessment (including unscheduled visits) prior to first dose of study treatment. For ECG, if multiple assessments are recorded on the same day, the mean of the multiple assessments will be assigned as the baseline value, and the latest ECG interpretation prior to the first dose of study medication will be used as the baseline ECG finding.

### 5.3. Multicentre Studies

- In this multicentre global study, enrolment will be presented by investigative site and country.
- The randomisation for this study is stratified by region, defined below, with consideration for standard of care medical practice.
  - USA
  - Argentina, Mexico and Brazil
  - Rest of World
- The same definition of region will be used for covariate adjustment in the statistical analysis.
- If there are insufficient subjects in each region for the planned statistical analysis, further combining of regions will be considered.

## 5.4. Examination of Covariates, Other Strata and Subgroups

### 5.4.1. Covariates and Other Strata

- Region and baseline OCS dose, expressed as prednisone equivalent dose, will be covariates in all statistical analysis. These covariates will be included as stratification variables for the Cochran-Mantel-Haenszel test and Wilcoxon Rank Sum test according to the table below. For parametric analysis models, region will be included as a fixed categorical effect and baseline OCS dose will be included as a fixed continuous effect.

Category	Covariates and / or Subgroups
Region	See Section 5.3. 
 
USA
 
Argentina, Mexico and Brazil
 
Rest of World
 

Baseline oral prednisone equivalent dose 	See Section 5.4.1.1 
 
0-≤20mg prednisone or equivalent
 
>20mg prednisone or equivalent
 

For parametric analysis models, baseline OCS dose will be included as a fixed continuous effect.

- If the percentage of subjects is small within a region, then the region categories may be refined prior to unblinding the trial.
- For analyses where a baseline value of the analysis variable is available this will also be included in the statistical analysis. These covariates will be included as stratification variables for the Cochran-Mantel-Haenszel test and Wilcoxon Rank Sum test, and as continuous fixed effects for all parametric analysis models.

#### 5.4.1.1. Derivation of Baseline Oral Prednisone Equivalent Daily Dose

- For each subject, a baseline oral prednisone equivalent daily dose (mg) will be derived prior to unblinding the randomisation codes for the study. Baseline oral prednisone equivalent dose will be identified from the concomitant medications page according to the following criteria:
  - Start date < Date of first dose of study treatment
  - Either “ongoing” or end date ≥ Date of first dose of study treatment
  - Route = “PO”
- Partial start and end dates will be handled as described in Section 16.7.2.1.
- Corticosteroids will be identified from the list of coded concomitant medications for the study, by merging with the GSK respiratory medication class (RMC) reference data set by component code. This reference data is created by dictionary specialists who identify a list of component terms for corticosteroids, which then undergo clinical review to ensure the correct classification is assigned.
- Subjects not receiving OCS therapy, i.e. subjects receiving cytotoxic and/or immunosuppressive HES therapy only at baseline, or subjects not receiving any HES

therapy, will be assigned a prednisone equivalent daily dose of 0 mg and will be categorised in the 0-≤20mg prednisone or equivalent group.

- The corticosteroid conversion factors in the table below will be used to scale each corticosteroid dose to a prednisone equivalent dose.

Medication Name	Scaling Factor
Betamethasone	8.33
Budesonide 	0
Cortisone	0.2
Dexamethasone	6.67
Deflazacort	0.83
Fluticasone 	0
Hydrocortisone	0.25
Methylprednisone	1.25
Meprednisone	1.25
Prednisone	1
Prednisolone	1
Prednisone acetate	1
Triamcinolone	1.25

Budesonide and fluticasone have negligible systemic exposure and will be classed as "Other HES therapy" rather than oral corticosteroid therapy.

- Where the frequency of the recorded corticosteroid dose is not once daily, the following calculations will be used to determine the daily dose.

Medication Frequency	Daily Dose Equivalent
BID	2 x dose
TID	3 x dose
QID	4 x dose
QOD	dose / 2
2XWK	(2 x dose) / 7
3XWK	(3 x dose) / 7
4XWK	(4 x dose) / 7
5XWK	(5 x dose) / 7

#### 5.4.2. Examination of Subgroups

- The subgroups in the table below are of interest in this study. A separate exploratory analysis of the primary endpoint within each subgroup will be carried out.
- Subgroup categories may be further collapsed if there are a small number of subjects in a treatment arm within a subgroup leading to model convergence issues.
- There is a biological rationale for potentially observing increased efficacy with increasing levels of baseline blood eosinophils. The role of blood eosinophil counts at baseline on the effectiveness of mepolizumab with respect to the primary endpoint will be further assessed based on a statistical model including baseline ( $\log_e$ ) blood eosinophil count as a continuous variable and an interaction with treatment term. Baseline blood eosinophil count is defined in Section 5.2. The analysis will also be adjusted for region and baseline OCS dose, as described in Section 5.4.1. Fractional polynomial models for the baseline blood eosinophil count may also be explored in order to find the best fitting model for the relationship.
- Differential treatment effects are not expected for any of the other subgroups listed below and therefore any differences in efficacy for mepolizumab compared to placebo observed in categories of these subgroups will be viewed as exploratory.

Subgroup	Categories
Age	
 
• 12-<18 years
 
• 18-64 years
 
• <math>\geq 65</math> years
 

Sex	
 
• Male
 
• Female
 

Race	
 
• Black or African American
 
• White
 
• Asian
 
• Other
 

Region	
 
• USA
 
• Argentina, Mexico and Brazil
 
• Rest of World
 

Baseline OCS	
 
• <math>0 \leq 20</math>mg prednisone or equivalent
 
• <math>> 20</math>mg prednisone or equivalent
 

Baseline blood eosinophils	
 
• Quartiles, rounded to 1 decimal place (GI/L); equivalent to rounding to the nearest 100 cells/<math>\mu</math>L
 

## 5.5. Multiple Comparisons and Multiplicity

When strong control of type I error is required for making inferences for the predefined secondary endpoints, multiplicity will be controlled using a hierarchical, closed testing procedure, according to the following hierarchy of endpoints:

1. Proportion of subjects who experience a HES flare during the 32-week study treatment period (primary endpoint)
2. Time to first HES flare
3. Proportion of subjects who experience a HES flare during Week 20 through Week 32
4. Rate of HES flares
5. Change from baseline in fatigue severity based on BFI item 3 (worst level of fatigue during past 24 hours) at Week 32

When strong control of type I error is required, statistical significance for an endpoint in the predefined hierarchy will be dependent on statistical significance for the previous endpoints in the hierarchy.

P-values for secondary endpoints will be provided both unadjusted and adjusted for multiplicity using the hierarchy of endpoints above.

## 5.6. Other Considerations for Data Analyses and Data Handling Conventions

Other considerations for data analyses and data handling conventions are outlined in the appendices:

Section	Component
16.3	Appendix 3: Assessment Windows
16.4	Appendix 4: Study Phases and Treatment Emergent Adverse Events
16.5	Appendix 5: Data Display Standards & Handling Conventions
16.6	Appendix 6: Derived and Transformed Data
16.7	Appendix 7: Reporting Standards for Missing Data
16.8	Appendix 8: Values of Potential Clinical Importance

## **6. STUDY POPULATION ANALYSES**

### **6.1. Overview of Planned Study Population Analyses**

The study population analyses will be based on the ITT population, unless otherwise specified. If the ITT population and the safety populations differ, study population analyses will also be produced for the safety population.

Study population analyses including analyses of subject's disposition, protocol deviations, demographic and baseline characteristics, prior and concomitant medications, exposure and treatment compliance (assessed by number of administrations of study treatment) will be based on GSK Core Data Standards. In addition, summaries of baseline HES therapy, most bothersome HES symptoms and steroid perception questionnaire will be produced; for the summary of the steroid perception questionnaire, only subjects completing the questionnaire who have a baseline oral steroid reported on their concomitant medication form will be summarised.

Details of the planned displays are presented in [Appendix 10](#): List of Data Displays.

## 7. EFFICACY ANALYSES

The target population for the primary estimand is as defined by the study inclusion/exclusion criteria and therefore the ITT population will be the primary population for all efficacy analyses.

### 7.1. Primary Efficacy Analyses

#### 7.1.1. Endpoint / Variables

The primary endpoint is the proportion of subjects who experience a HES flare during the 32-week study treatment period.

A HES flare is defined as either:

- a) A HES-related clinical manifestation based on a physician-documented change in clinical signs or symptoms resulting in the need for either of the following:
  - An increase in the maintenance OCS dose by at least 10mg/day for 5 days
  - An increase in or addition of any cytotoxic and/or immunosuppressive HES therapy*or*
- b) Receipt of two or more courses of blinded active OCS during the treatment period.

HES flares meeting definition a) will be captured on the ‘flare details’ page in the eCRF.

An increase in blood eosinophils above the pre-defined threshold level (2 x baseline value or baseline value + 2500 cells/ $\mu$ L) without any other clinical manifestations during the study will lead to administration of blinded active OCS treatment (see Section 2.2). If a subject receives a second course of blinded active OCS during the 32-week treatment period, the subject will be considered to be experiencing a flare. The container list for the blinded OCS treatment (indicating which container numbers contained active OCS and which contained placebo OCS) will be used to define HES flares meeting endpoint definition b).

#### 7.1.2. Summary Measure

The difference between mepolizumab and placebo in the proportion of subjects with HES flare during the 32-week study treatment period.

#### 7.1.3. Strategy for Intercurrent (Post-Randomization) Events

##### 7.1.3.1. Primary Estimand

The primary treatment effect to be estimated (estimand) will be the ‘treatment policy’ effect of initial randomised treatment. A treatment policy strategy will be used for the intercurrent events of a) discontinuation of study medication and b) receipt of alternative HES medications.

The study is designed to continue to collect data on HES flares for subjects who prematurely discontinue from their randomised study treatment. All data on HES flares collected for these subjects will be included in the primary analysis. Subjects who withdraw from the study prior to Week 32 (Visit 11) and therefore have missing data on HES flares will be included in the primary analysis as treatment failures, i.e. for the primary comparison, a subject will be classed as not experiencing a HES flare only if they have no flares reported and complete Week 32 (Visit 11).

Sensitivity analyses will be performed on the ITT population to examine the potential impact of the missing data:

- Subjects withdrawing from the study prematurely prior to reporting a HES flare, with the primary reason for treatment withdrawal reported as AE or Lack of Efficacy, will be classed as experiencing a HES flare in the analysis. Subjects withdrawing from the study prematurely with any other reason for treatment withdrawal will be included as having a flare if one is recorded prior to study withdrawal, and as not having a flare if no flare is recorded prior to study withdrawal.
- Subjects withdrawing from the study prematurely will be included as having a flare if one is recorded prior to study withdrawal, and as not having a flare if no flare is recorded prior to study withdrawal.

#### **7.1.3.2. Supplementary Estimand**

A supplementary estimand using the ‘while on treatment’ strategy will be assessed for the intercurrent event of discontinuation of study medication.

Subjects discontinuing from study treatment prematurely will be included as having a HES flare if a flare is recorded with an onset date equal or prior to 28 days after the last dose of study treatment, and not having a flare otherwise.

#### **7.1.4. Statistical Analyses / Methods**

Details of the planned displays are provided in [Appendix 10](#): List of Data Displays and will be based on GSK data standards and statistical principles.

A summary of the number and percentage of subjects with HES flares will be produced by treatment group. The total number of HES flares in each treatment group will also be presented. The summary will include all HES flares, as well as a separate breakdown of HES flares meeting definition a) and b) (see Section 7.1.1). A plot of the cumulative number of HES flares over time in each treatment group will be produced.

### 7.1.4.1. Statistical Methodology Specification

Primary Statistical Analyses
Endpoint

 
Proportion of subjects who experience a HES flare during the 32-week study treatment period.
 

Model Specification

 
Cochran-Mantel-Haenszel test stratified by baseline OCS dose (0-≤20mg/day and >20mg/day prednisone or equivalent) and region.
 
Supplemented by a logistic regression analysis adjusting for covariates of baseline OCS dose (continuous scale), region, and treatment.
 

Model Checking & Diagnostics

 
To examine the fit of the logistic regression model, deviance residuals will be calculated and plotted.
 

Model Results Presentation

 
Number of subjects analysed in each treatment group.
 
Number of subjects with ≥1 HES flare or who withdraw from the study prior to Week 32 (Visit 11). 
 
Number of subjects with ≥1 HES flare.
 
Number of subjects with no HES flare who withdraw from the study prior to Week 32 (Visit 11).
 
 
 
Number of subjects with no HES flare who complete Week 32 (Visit 11).
 
p-value from Cochran-Mantel-Haenszel test.
 
Odds ratio and 95% Confidence Interval (CI) from logistic regression model.
 
p-value from logistic regression model.
 

Subgroup Analyses

 
A logistic regression analysis will be fitted separately within each subgroup of interest defined in Section 5.4.2.
 
Odds ratios and 95% confidence intervals from the logistic regression model will be presented. Analysis will be descriptive only; no p-values will be presented for the subgroup analyses. If the number of subjects in each subgroup category are small, confidence intervals may also be omitted.
 

Sensitivity and Supportive Statistical Analyses

 
A supplementary estimand using the ‘while on treatment’ strategy for intercurrent events will be assessed.
 
The primary analysis will be repeated using the PP population.
 
Sensitivity analyses for the primary estimand to assess the impact of missing data will be performed using the ITT population as follows: 
 
Subjects withdrawing from the study prematurely prior to reporting a HES flare, with the primary reason for treatment withdrawal reported as AE or Lack of Efficacy, will be classed as experiencing a HES flare. Subjects withdrawing from the study prematurely with any other reason for treatment withdrawal will be included as having a flare if one is recorded
 
 
 

**Primary Statistical Analyses**

- prior to study withdrawal, and as not having a flare if no flare is recorded prior to study withdrawal.
- Subjects withdrawing from the study prematurely will be included as having a flare if one is recorded prior to study withdrawal, and as not having a flare if no flare is recorded prior to study withdrawal.
  - The sensitivity of the results of the primary estimand to inclusion of subjects from site PPD in Mexico will be investigated. An investigation of this site was conducted by GSK following anomalies in pulmonary function test (PFT) data generated by this site for a GSK study with a different investigational product (Study 207597). The report concluded that “there was diminished confidence and trust in the integrity of the data generated at this site and this loss of trust extended to other aspects of study conduct at this site”. Therefore, a sensitivity analysis of the primary estimand excluding the two subjects from site PPD will be performed.

**7.1.5. Exploratory Modelling of Primary Endpoint**

The role of baseline blood eosinophil counts on the effectiveness of mepolizumab with respect to the proportion of subjects who experience a HES flare during the 32-week study treatment period will be investigated. A logistic regression model will be fitted, including baseline blood eosinophils fitted on the  $\log_e$  scale as a continuous covariate as well as a treatment-by-baseline blood eosinophils interaction term, in order to predict the odds ratio for mepolizumab vs placebo for each level of the baseline blood eosinophil count. The analysis will also be adjusted for region and baseline OCS dose, as described in Section 5.4.1. Fractional polynomial models may also be explored in order to find the best fitting model for the relationship.

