4.2. Treatment Arms and Duration

- The study is comprised of a screening period of up to approximately 4 weeks followed by a 32-week study treatment period and up to 8-week additional follow-up period (12 weeks after the last dose of study treatment).
- Approximately 80 subjects who are able to maintain a stable regimen of HES therapy for the 4 weeks prior to Visit 2 will be randomized in a 1:1 ratio to receive either 300 mg mepolizumab *or* placebo SC every 4 weeks while continuing their HES therapy. The sample size may be increased up to a maximum of 120 subjects in total (Section 9.2.3). The same regimen of HES therapy will be maintained throughout the 32-week study treatment period unless there is worsening of symptom(s) that requires an increase in therapy. A reduction in dose for safety reasons, with return to the original dosing regimen if possible, is permitted in consultation with the GSK Medical Monitor.

- The final dose of study treatment will be administered at Visit 10 (Week 28) with completion of the study treatment period achieved at the next 4-weekly visit. At Visit 11 (Week 32), subjects will complete the end-of-treatment assessment (4 weeks after the last dose).
- Subjects who withdraw from study treatment prematurely should continue in the study per protocol (including HES flare-related assessments) until 32 weeks from randomization.
- For subjects whose last dose of study treatment is on Visit 9 (Week 24) or Visit 10 (Week 28) *and* who do not continue with open-label mepolizumab after completing Visit 11 assessment (32 weeks from randomization), there will be up to 8-week additional follow-up period, concluding with the 12 weeks post-last dose follow-up visit (Visit 12).
- Subjects will be eligible to be considered to receive open-label mepolizumab 300 mg SC every 4 weeks after *either*:
 - i. Completion of the treatment period in the 200622 study
 - or*
 - ii. If the subject was withdrawn from study treatment prematurely during the 200622 study, but continued in the study per protocol (including HES flare-related assessments) until 32 weeks from randomization.

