9.2. Sample Size Considerations

9.2.1. Sample Size Assumptions

This study is designed to test the superiority of mepolizumab versus placebo.

The primary efficacy endpoint is the proportion of subjects who experience an HES flare during the 32-week study treatment period. The power calculation assumes that 60% of subjects on placebo will experience an HES flare during the 32-week study treatment period. With a two-sided 5% level of significance and a sample size of 40 randomized subjects per arm, the null hypothesis will be rejected if the observed proportion of patients with an HES flare on placebo is 60% and on mepolizumab is 35% or less. If the true population proportion of subjects who would experience an HES flare during the 32-week study treatment period on placebo is 60% and on mepolizumab is 22%, the study has 90% power for demonstrating a statistically significant result for this assumed true population effect.

This endpoint is novel, and has not explicitly been used in clinical trials of HES. There is therefore little previous data on which to base estimates of the number of subjects who will experience an HES flare during the 32-week study treatment period.

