9.2.3. Sample Size Re-estimation or Adjustment

While the estimate of 60% of placebo subjects and 22% of mepolizumab subjects having an HES flare during the 32-week study treatment period is felt by clinical experts to be reasonable for this population, the proportion of subjects who have an HES flare will be monitored, blinded to treatment, and if the blinded overall proportion is predicted to be <30% the sample size may be increased up to a maximum of 60 subjects per group (total 120 subjects). The planned increase to sample size will depend on the observed blinded overall proportion of subjects as follows:

Blinded overall proportion ¹ (%)	N per group
≥30	40 (no increase)
27.5 – 30	45
25-<27.5	50
<25	60

¹Proportion of subjects who have an HES flare during the 32-week study treatment period.

The decision to increase the sample size will be made when at least 30 subjects per arm have been randomised. The blinded overall proportion of subjects who have an HES flare will be calculated based on the HES flare data available in the CRF. This will include all HES flares meeting flare endpoint definition ‘a)’ in Section 7.3.1. The number of HES flares due to flare endpoint definition ‘b)’ is expected to be small, therefore in order to maintain the blood eosinophil blinding, HES flares due to subjects receiving two or more courses of blinded active OCS will not be included in the calculation of the blinded overall proportion.

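### The baseline-eosinophil interaction curve can show a gradient produced by the flare definition, because flare definition (b) is triggered by a function of the same baseline count

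*SAP*

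**What the plan says.** The primary endpoint counts a flare under either of two definitions (Protocol 7.3.1, SAP 7.1.1). Definition (a) is a clinical worsening that leads to a specified escalation of HES therapy. Definition (b) is at least two courses of blinded active OCS. A course is triggered when the count reaches the "pre-defined threshold level (2 x baseline value or baseline value + 2500" cells/µL), with baseline taken at randomization (Protocol 6.4). A second course can follow at the recheck about two weeks later if the count is still at or above the trigger.

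SAP 7.1.5 regresses this combined outcome on log baseline eosinophil count, adjusted for region and baseline OCS dose, with a "treatment-by-baseline blood eosinophils interaction term, in order to predict the odds ratio for mepolizumab vs placebo" at each level of baseline. The result is Figure 2.5, and fractional polynomials may be tried. Table 2.14 gives the endpoint by baseline-eosinophil quartile. SAP 5.2 defines the baseline count as the last central laboratory value before the first dose. This is the only subgroup factor for which SAP 5.4.2 states a prior expectation: "There is a biological rationale for potentially observing increased efficacy with increasing levels of baseline blood eosinophils".

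The split into definitions (a) and (b) is planned by arm only, as counts (SAP 7.1.4) and median rates (SAP 7.4.4.1). SAP 7.6.1 compares the arms on reaching the threshold. No version of 7.1.5 or Table 2.14 uses definition (a) alone.

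**The concern.** The baseline count enters the analysis twice: as the modifier, and inside the rule that decides who has a definition (b) event. If the chance of meeting that rule changes with baseline, and such events occur almost only on placebo, the treatment odds ratio changes with baseline as well, even when the drug works equally well at every count.

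What is at stake is interpretation. The planned output is a predicted odds ratio across the baseline range, so the shape of the curve will be seen whatever the interaction p-value. A reader could take a slope produced by the endpoint rule as evidence about which patients benefit more, or could miss a real slope that the rule has cancelled.

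**Working it through.** **1. The plan's own figure.** The documents give no figure for the interaction model, so the check starts from the design. Protocol 9.2.1 has: "With a two-sided 5% level of significance and a sample size of 40 randomized subjects per arm"; and, for true proportions, "on placebo is 60% and on mepolizumab is 22%, the study has 90% power". The continuity-corrected formula for 60% against 22% gives 39 per arm, and exact power at 40 per arm is 91.9%. The stated rejection boundary also reproduces: 24/40 against 14/40 gives p = 0.043 to 0.044, and 24/40 against 15/40 gives p = 0.073 to 0.074. The implied odds ratio is (0.22/0.78)/(0.60/0.40) = 0.188.

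**2. The trigger against baseline B.** Reading the two conditions as whichever is reached first, the trigger relative to baseline is min(2B, B + 2500)/B.

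| B (cells/µL) | Trigger | Trigger/B | Rise needed |
|---|---|---|---|
| 1000 | 2000 | 2.00 | 100% |
| 2500 | 5000 | 2.00 | 100% |
| 4000 | 6500 | 1.63 | 63% |
| 5000 | 7500 | 1.50 | 50% |
| 8000 | 10500 | 1.31 | 31% |

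The rule is a constant doubling up to 2500; only above that does the relative rise fall.

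**3. Which arm has these events.** Protocol 4.5 predicts 100 to 500 cells/µL on mepolizumab for baselines of 1000 to 8000. The lowest trigger in that range is 2000, four times the upper end of the prediction. Definition (b) events should therefore be almost confined to placebo.

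**4. Simulation with no true modification.** The definition (a) odds ratio and the proportional eosinophil reduction were held constant across baseline, and overall flare proportions were set to 60% and 22%. Assumed, because the documents are silent: baseline median 2000 with log SD 0.7, mepolizumab count ratio 0.12, the response to OCS, and the within-subject variability shown below. Region, baseline OCS dose and withdrawal were left out. The coefficient is per log unit of baseline; negative means a stronger apparent effect at high counts.

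| Assumed variation in counts | Coefficient, all flares | Fitted OR at 1000, at 8000 | Coefficient, (a) only | Placebo flares by (b) only |
|---|---|---|---|---|
| Proportional around baseline, log SD 0.3 | -0.28 | 0.24, 0.13 | 0.01 | 2.9% |
| Same, log SD 0.5 | -0.50 | 0.30, 0.10 | -0.02 | 13.7% |
| Proportional random walk, step SD 0.15 | -0.22 | 0.23, 0.14 | 0.00 | 3.7% |
| Baseline is one noisy reading, log SD 0.3 | -0.12 | 0.21, 0.16 | -0.01 | 4.3% |
| Same, central baseline may be below 1000 | -0.03 | 0.19, 0.18 | -0.01 | 5.1% |
| One noisy reading, log SD 0.5 | +0.09 | 0.17, 0.20 | 0.01 | 13.9% |
| Same, central baseline may be below 1000 | +0.30 | 0.14, 0.27 | 0.00 | 18.8% |
| Additive, SD 600 cells/µL | +0.05 | 0.18, 0.20 | 0.02 | 0.3% |
| Additive, SD 1000 cells/µL | +0.22 | 0.16, 0.25 | -0.01 | 3.0% |

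The sign has a simple explanation. If counts vary in proportion to the recorded baseline, the smaller relative rise above 2500 makes high-baseline placebo subjects trigger more often. If baseline is one noisy reading, a low value tends to sit below the subject's usual level and doubles easily. If variation is additive, a low baseline needs the smaller absolute rise. The last two work against the first. The rows with baseline below 1000 are relevant because SAP 2.2 lets a local laboratory result satisfy the entry criterion. A further simulation with other assumed settings gave -0.72 to +0.47 for all flares, and again -0.02 to +0.02 for definition (a).

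**5. Test size.** With 1,500 simulated trials per row, the 5% interaction test rejected in 4.3% to 7.9% at N = 80 and 4.5% to 9.4% at N = 120, the maximum in Protocol 9.2.3. Where flares by (b) only were about 5% of placebo or fewer, the range was 4.3% to 5.9%.

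**The case against.** The strongest reply is that SAP 7.1.5 asks how the effect on the primary endpoint varies with baseline. If high-count placebo subjects do receive more repeat OCS courses, the combined outcome really is modified, and the model estimates that correctly. This stands: the issue is attribution between the two definitions, not a biased estimate of the stated quantity.

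The effect may also be small. Protocol 9.2.3 expects few definition (b) flares. In a low-variability simulation (log SD 0.15 to 0.2, definition (a) odds ratio 0.345, median baseline 2500) the coefficient was -0.17 to -0.30, against a standard error of about 0.7 at N = 100: 0.17/0.7 = 0.24 and 0.30/0.7 = 0.43 standard errors. The analysis is exploratory, lies outside the testing hierarchy, and the quartile table carries no p-values. All this stands and limits the weight of the point. None of it separates the two definitions by baseline.

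Definition (a) alone is not a clean comparator either. Its null coefficients above follow from how it was simulated. Blinded active OCS may suppress symptom flares; when OCS was assumed to cut the next month's definition (a) hazard by 70%, that model acquired coefficients of +0.03 to +0.10, and -0.05 in one setting. This supports showing the models side by side and not replacing one with the other.

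A reader might infer that the artefact must favour high counts, matching the SAP's biological rationale. The documents do not support that. They give no within-subject variability, the threshold creates no relative gradient at or below 2500, and plausible assumptions reverse the sign.

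**Conclusion.** The coupling is established from the documents: one baseline count, or two adjacent readings of it, both sets the definition (b) trigger and serves as the effect modifier in SAP 7.1.5 and Table 2.14. The odds-ratio curve can therefore show a gradient that comes from the endpoint definition. Its direction and size are not established. Across the tabulated assumptions the coefficient ran from -0.50 to +0.30 per log unit, which moves the fitted odds ratio between 1000 and 8000 cells/µL from 0.30 to 0.10 at one extreme and from 0.14 to 0.27 at the other. The interaction test stays essentially at its nominal level when definition (b) flares are few, and the primary analysis is not touched. This is a minor improvement to an exploratory analysis, worth making because the sign is unknown and readers could not correct for it themselves.

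**What to change.** In SAP 7.1.5 and Table 2.14, add the same analysis with definition (a) flares only as the outcome, keeping the covariates and the rule for early withdrawal unchanged, and present it beside the all-flare version. Add a table of definition (b) flares by arm and baseline-eosinophil category. State in advance that a gradient will be attributed to a differential effect on symptom flares only if it also appears in the definition (a) version, with a note that triggered OCS may slightly affect definition (a). The flare definition, the trigger and the primary analysis stay as they are.

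The cost is one repeated exploratory model and table, plus a count table, all on data already derived. The definition (a) model has slightly fewer events and so slightly wider intervals.
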